4.3. Study Plan and Process

The study comprises a screening period (Day -28 to -1), a treatment period (28 days/cycle, including a single dose PK study period [Day 1-7]), and a safety follow-up period (28 days after the last dose).

4.3.1. Screening/Baseline Period (Day -28 to Day -1)

Informed consent must be obtained before all the specific study procedures in this clinical trial. Subject is eligible for participation in this clinical trial after reviewing the inclusion and exclusion criteria. Candidates could be re-screened once if they did not fulfill the entry eligibility (failed screening) at the first screening visit. Subjects need to re-sign the ICF and obtain a new screening number during re-screening.

4.3.2. Treatment Period

♦ PK Sampling:

During the single dose PK study period, venous blood (3 mL each) will be collected within 1 h before the first dose, and 0.5 h, 1 h, 2 h, 3 h, 4 h, 6 h, 8 h, 12 h, 24 h, 48 h, 72 h, and 96 h after the first dose.

During the first cycle treatment period, venous blood (3 mL each) will be collected within 1 h before dosing on C1D8, C1D15, and C1D28, and 0.5 h, 1 h, 2 h, 3 h, 4 h, 6 h, 8 h, 12 h, 24 h after dosing on C1D28.

♦ Safety Evaluation:

The safety evaluation includes physical examinations, vital signs, laboratory evaluations, ECG, ophthalmological examination, and AE collection. Please refer to flow chat for detail safety visit schedules.

♦ Efficacy Evaluation:

The anti-tumor activity will be evaluated according to the RECIST 1.1 criteria. Tumor imaging assessments will be performed every 8 weeks (\pm 7 days) until disease progression, death, withdrawal of informed consent, or termination of treatment. Subjects who discontinue treatment for reasons other than disease progression or death should continue with imaging assessments per

protocol-defined schedule until disease progression, death, or withdrawal of informed consent, whichever occurs first.

If the imaging result shows a CR or PR for the first time, it is necessary to repeat the tumor imaging at least 4 weeks later to confirm the response. Imaging assessments will be performed according to the aforementioned schedule regardless of the efficacy confirmation scan.

If a subject terminates 3D185 treatment due to symptomatic deterioration/disease progression, the Investigator should continue to perform imaging scan until documented radiographic disease progression.

♦ Tumor Tissue Specimen:

For subjects with benefit from receiving 3D185 monotherapy (CR or PR or SD), it is recommended to obtain the disease-related archived tumor tissue or fresh tumor biopsy as much as possible with their consent to explore the relationship between the anti-tumor activity of 3D185 and FGFR alterations in tumor tissue.

♦ Safety Follow-up:

Safety follow-up will be performed on Day 28 (±7 days) after the last dose. Subjects in this visit will receive safety assessments, including evaluation of AEs, vital signs, physical examinations, ECG, ophthalmological examination, laboratory tests, etc.

The detailed flow chart of this study is shown in Table 3.

Table 3Study Flow Chat

Date			Treatment Period											Follow-up	
Items	Scree	ening	Single dose PK study period				od	1 st Treatment cycle				2 nd Treatment cycle		Addition al cycles	28 Days after last dose (±7 days) ¹⁸
	Days-28 to -1	Days-7 to -1	C0D1	C0D2	C0D3	C0D4	C0D5	C1D1	C1D8	C1D15	C1D28	C2D15	C2D28	CxD28	
Informed Consent ¹	X														
Inclusion/Exclusion Criteria		X													
Demographics/Med ical History	X														
Tumor History/Treatment History ²	X														
Physical Examination ³		X						X	X	X	X	X	X	X	x
ECOG Performance Status		X									X		X	X	x
Vital Signs		X						X	X	X	X	X	X	X	x
CBC with Differential ⁴		X						X	X	X	X	X	X	X	X
Comprehensive Serum Chemistry Panel ⁵		X						x	X	X	X	X	X	X	X

Date								Trea	tment P	eriod					Follow-up
Items	Screening		Single dose PK study period			1 st Treatment cycle				2 nd Treatment cycle		Addition al cycles	28 Days after last dose (±7 days) ¹⁸		
	Days-28 to -1	Days-7 to -1	C0D1	C0D2	C0D3	C0D4	C0D5	C1D1	C1D8	C1D15	C1D28	C2D15	C2D28	CxD28	
Coagulation Parameters ⁶		X									X			X (every 8 weeks ∄7 days after C3D28)	X
Urinalysis ⁷		X						X	X	X	X	X	X	X	x
12-Lead ECG ⁸		X	X					X	X	X	X	X	X	X	x
Ophthalmological examination ⁹		x									x			X (every 8 weeks ±7 days after C3D28)	x
Pregnancy Test - Serum β-HCG ¹⁰		X													
Echocardiography	X					1	1	X (clin	ically ind	licated)	L		1	L	X
Tumor assessment ¹²	X												x	X (every 8 weeks ∄ days after C4D28)	
Concomitant medications ¹³	X	X		X						X					

Date				Treatment Period									Follow-up		
Items	Scree	ening	ning Single do			Single dose PK study period			1 st Treatment cycle			2 nd Treatment cycle		Addition al cycles	28 Days after last dose (±7 days) ¹⁸
	Days-28 to -1	Days-7 to -1	C0D1	C0D2	C0D3	C0D4	C0D5	C1D1	C1D8	C1D15	C1D28	C2D15	C2D28	CxD28	
Review Adverse Events ¹⁴				X								X			
Pharmacokinetics			x	x	X	x	x		X	X	x				
Virologic examination ¹⁶	X														
Archival Tumor Tissues ¹⁷						•			X						

Notes:

- 1. Informed consent must be obtained prior to all the specific study procedures in this clinical trial. And the date of signature can be prior to the 28-day screening window period. Subjects who failed screening may be screened again but need to re-sign the informed consent form and obtain a new screening number.
- 2. The latest anti-tumor treatment history must be recorded.
- 3. Physical examination includes examination of whole human body systems.
- 4. CBC with differential: whole blood count (absolute value) includes red blood cell count, white blood cell counts, and differential counts (neutrophils, lymphocytes, monocytes, eosinophils, and basophils), platelet count, hemoglobin, and hematocrit. This test should be completed within 7 days prior to the first dose. It is unnecessary to repeat on C0D1 if the subject has no clinical signs and indications. This test should be completed before dosing within 3 days prior to days C1D1, C1D8, C1D15, C1D28, C2D15, C2D28, CxD28, and safety follow-up period. An unscheduled exam can be performed if there are clinical indications.
- 5. Blood biochemistry includes ALT, AST, total bilirubin, BUN (urea nitrogen) or urea, Cr (creatinine), blood glucose, potassium, sodium, chlorine, calcium, phosphate, magnesium, total protein, albumin, albumin/globulin ratio, LDH (lactate dehydrogenase), and ALP (alkaline phosphatase). This test should be completed within 7 days prior to the first dose. It isn't required to repeat on C0D1 if the subject has no clinical signs and indications. This test should be completed before dosing within 3 days prior to days C1D1, C1D8, C1D15, C1D28, C2D15, C2D28, CxD28 and safety follow-up period. Among them, phosphate levels will also be used for PD analysis.
- 6. Coagulation functions include prothrombin time (PT), APTT, and INR. This test should be completed within 7 days prior to the first dose. It isn't required on C0D1 if the subject has no clinical signs and indications. This test should be completed before dosing within 3 days prior to C1D28, every 8 weeks (±7 days) in additional cycles, and safety follow up visit.

- 7. Urinalysis includes specific gravity, pH, white blood cells, red blood cells, proteins, glucose, ketones, and casts. This exam should be completed within 7 days prior to the first dose. If urine protein ++, it is recommended to test 24-hour urine protein quantitation as soon as possible (if within 72 hours). It isn't required on C0D1 if the subject has no clinical signs and indications. This test should be completed before dosing within 3 days prior to days C1D1, C1D8, C1D15, C1D28, C2D15, C2D28, CxD28, and safety follow-up period.
- 8. The 12-lead ECG should be completed within 7 days of the first dose. This test should be performed at 2 hours (±5 min) after dosing on C0D1 and C1D28. It also should be completed before dosing within 3 days prior to days C1D1, C1D8, C1D15, C2D15, C2D28, CxD28, and safety follow up visit.
- 9. Ophthalmological examination includes non-contact intraocular pressure, slit lamps, fundus examinations, and optical coherence tomography. The examination should be completed within 7 days prior to the first dose. It isn't required on C0D1. This test should be completed before dosing within 3 days prior to C1D28, every 8 weeks (±7 days) in additional cycles, and the safety follow-up period.
- 10. A serum pregnancy test should be completed at the screening period. Female subjects at childbearing age should complete the examination within 7 days prior to the first dose.
- 11. Echocardiography should be performed during the screening period, the treatment period (if clinically indicated), and the safety follow-up period.
- 12. Baseline tumor assessment should be completed within 28 days prior to the first dose. It is recommended to perform CT or MRI of the chest, abdomen, and pelvic at baseline. Subjects with known or suspected brain metastases should have a CT or MRI of the brain at baseline. If there are clinical indications or suspicious lesions in other areas, tumor imaging evaluation must also be performed. Baseline assessment and post-treatment efficacy assessment will be performed using the same method and as much as possible by the same Investigator (RECIST 1.1 criteria). Tumor imaging assessment (CT or MRI) should be performed every 8 weeks (#7 days) from C1D1 until disease progression, death, withdrawal of informed consent, or termination of treatment. Subjects who discontinue treatment for reasons other than disease progression or death should continue with imaging assessments per protocol-defined schedule until disease progression, death, or withdrawal of informed consent, whichever occurs first. If the imaging result shows a CR or PR for the first time, it is necessary to repeat the tumor imaging at least 4 weeks later to confirm the response. If clinically indicated, the Investigator can perform an unscheduled tumor assessment.
- 13. Concomitant medications include any prescription and OTC medications. During the baseline screening, all medications that used by the subjects should be recorded from 28 days prior to the first dose to safety follow-up 28 days after the last dose. And after safety follow-up, record other anti-tumor drugs only.
- 14. AEs will be collected from C0D1 to 28 days after the last dose. After signing the informed consent form, any SAE associated with the protocol required operation that occurs before the start of dosing should also be reported. Investigational product related AEs and investigational product unrelated SAEs or life-threatening AEs will be followed up until recovery to Grade 0-1 or baseline status, or the Investigator has assessed that it is in a stable status, or confirmed not investigational product related AE, or subject has begun a new anti-tumor treatment, lost follow-up, or withdraw informed consent. Investigational product related SAEs occurred after safety follow-up visit should also be recorded, reported and follow up.
- 15. PK blood sample during single dose treatment period will be collected within 1 h before dosing and 0.5 (±5 min), 1 (±5 min), 2 (±5 min), 3 (±5 min), 4 (±5 min), 6 (±5 min), 8 (±5 min), 12 (±5 min), 24 (±10 min), 48 (±10 min), 72 (±10 min), and 96 (±10 min) hours after dosing. PK sampling during multiple dose treatment period will be performed within 1 h before dosing on C1D8, C1D15 and C1D28, and at 0.5 (±5 min), 1 (±5 min), 2 (±5 min), 4 (±5 min), 6 (±5 min), 12 (±5 min), and 24 (±10 min) after dosing on C1D28. Each time will collect venous blood 3 mL. PK will be tested by a central laboratory. Details see Laboratory Manual.
- 16. Virological examinations (including HBV DNA quantification and HCV antibody testing) should be tested during screening period. To avoid repeat exam, the results before informed consent are acceptable if within 28 days prior to the first dose.
- 17. For subjects with benefit from receiving 3D185 monotherapy (CR or PR or SD), it is recommended to obtain the disease-related archived tumor tissue or fresh tumor biopsy as much as possible with their consent to explore the relationship between anti-tumor activity of 3D185 and FGFR alterations in tumor tissue.
- 18. Subjects who completed or prematurely discontinued investigational product therapy should return to the study center for safety assessment on 28 (±7) days after the last dose or before starting other anti-tumor treatments, whichever occurs first. For subjects who have completed investigational product therapy but have not assessed disease progression, it is recommended to continue the tumor imaging assessment during this follow-up.

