	18. Female subjects in pregnancy or lactation. Male subjects or female subjects at reproductive ages who are unwilling to receive effective contraceptive measures.		
	19. Subjects who are judged by the Investigator to be unsuitable for this study.		
Study	• The study objectives have been achieved;		
Termination	• The incidence and severity of AEs in this study suggest that it		
Criteria	is not appropriate to continue this clinical trial.		
	Study treatment Completion Criteria (Eligible for any of the following criteria):		
	♦ Progressive disease (RECIST 1.1);		
	♦ Death.		
	Early treatment discontinuation criteria meeting any of the following criteria):		
	1) Subject withdrew informed consent;		
Criteria of treatment	2) Unacceptable treatment toxicity;		
Discontinuation	3) Receive other anti-cancer therapies;		
	4) The Investigator determines it is in the best interest of the		
	subject to discontinue the investigational product treatment;		
	5) Poor compliance or severe protocol violations, and have an		
	impact on drug tolerance, safety, or PK evaluation;		
	6) Pregnancy during the study period;		
	7) Lost to follow-up;		
	8) Others.		

Primary endpoint:

The safety and tolerability of 3D185:

The safety and tolerability of 3D185 will be evaluated based on the frequency and attribute of DLT in the first 35 days after the first dose and the incidence of all AEs and serious adverse events (SAEs) during study period (including screening period, treatment period, and safety follow-up period) (according to NCI CTCAE v4.03).

Secondary Endpoints:

- 1. PK evaluation: including but not limited to, C_{max} , T_{max} , $AUC_{0-24 h}$, $AUC_{0-96 h}$, $AUC_{0-\infty}$, $t_{1/2}$, CL and Vd.
- 2. PD evaluation: PD parameters will be assessed by analyzing the change in serum phosphate levels relative to baseline level over time (Serum biochemistry test)
- 3. Efficacy evaluations: CR, PR, SD, and disease progression will be evaluated, and objective response rate (ORR) (CR+PR) and disease control rate (DCR) (CR+PR+SD) will be determined according to RECIST version 1.1 criteria.

Exploratory Endpoint:

4. The relationship between the anti-tumor activity of 3D185 and the tumor FGFR alterations.

Statistical analysis

The final sample size for the dose escalation study will depend on the number of dose levels evaluated and the occurrence of DLT at each dose cohort. The maximum sample size is expected to be 42 subjects.

Analysis Population:

1. Full Analysis Set (FAS)

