2.3. Benefit-risk assessment

3D185 is a highly potent and highly selective FGFR1-3 inhibitor. Since this novel drug is still in the initial stage of clinical development, the available safety and efficacy data mainly comes from preclinical data, and clinical research results of similar drugs. The clinical experience of 3D185 still needs further accumulation.

To date, most of the significant AEs associated with similar drugs that have been observed in the clinical studies are mild to moderate and reversible, such as hyperphosphatemia, nail and mucosal disorders, fatigue, reversible retinal pigment epithelial detachment (RPED), elevated transaminases, hypercalcemia, dyspnea, etc^[10-17]. It was reported that the ORR of FGFR inhibitors in subjects with solid tumors (screened or unscreened) was at the range of 0% to 37.5%, and the DCR was at the range of 22.2% to 91.3%. (Table 1 and Table 2)

NCT	Phases	Drugs	Tumor Types	Results
NCT01212107	Phase 1	LY2874455	Gastric Cancer & NSCLC (no selected)	Gastric cancer (n=29), no ORR; NSCLC (n=24), no ORR.
NCT01703481	Phase 1	JNJ-42756493	Urothelial cancer and other cancers	23 evaluable cases, ORR: 21.7%; DCR: 91.3% (4 PR and 1 unconfirmed PR; 16 SD).
NCT01703481	Phase 1	JNJ-42756493	Cholangiocarcinoma	n=11; ORR: 27.3%; DCR: 54.5%.
NCT02365597	Phase 2	JNJ-42756493	Urothelial cancer	N=87; ORR=32.3%; DCR=78.2%
NCT02393248	Phase 1/2	INCB054828	Cholangiocarcinoma and other cancers	n=49 (part 1, n=22; part 2, n=27). Part 2 ORR: 11%; DCR :37%。
NCT01948297	Phase 1	Debio 1347	Solid tumors	n=57. PR: 6 (8.45%); SD: 16 (28.07%)
			Squamous Lung Cancer	n=36. PR: 11.1%; DCR: 50%
NCT01004224	Phase 1	BGJ398	Bladder/urothelial cancer	n=8. PR: 37.5%; DCR: 75%
			Breast cancer	n=32; SD: 31%
NCT02150967	Phase 2	BGJ398	Cholangiocarcinoma	N=61. ORR: 14.8%; DCR: 75.4%
NCT01976741	Phase 1	BAY 1163877	Bladder/urothelial cancer	n=8; PR: 37.5% (2 FGFR3 mutation or fusion, 1 wild type)
NCT01752920	Phase 1/2	ARQ 087	Cholangiocarcinoma	n=35. PR: 17%; SD: 63%
NCT00979134	Phase 1	AZD4547	Squamous cell carcinoma	n=13. PR: 7.7%; SD: 38.5%
NCT00979134	Phase 1	AZD4547	Gastric cancer	n=13. PR: 7.7%; SD: 30.8%
NCT01795768	Phase 2	AZD4547	Esophageal cancer	n=9 (FGFR2); PR: 33.3%; SD: 22.2%
			Breast cancer	n=8 (FGFR1); PR: 12.5%; SD: 25%
NCT02965378	Phase 2/3	AZD4547	Squamous cell carcinoma	n=27. PR: 8% (4% unconfirmed); SD 48%.

Table 1 Anti-Tumor Activity of Different FGFR Inhibitors

Indications	Types (Frequency)	Drugs	NCT	ORR	SD

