3.2. Secondary Objectives

- c. To preliminarily characterize the PK and the PD profiles of single and multiple-dose of 3D185 monotherapy in subjects with advanced solid tumors;
- d. To preliminarily evaluate the anti-tumor activity of 3D185 monotherapy in subjects with advanced solid tumors.

3.3. Exploratory Objective:

e. To explore the relationship between the anti-tumor activity of 3D185 monotherapy and the FGFR alterations in subjects with advanced solid tumors.

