7.4.2. Efficacy Assessments

Baseline tumor assessment should be completed within 28 days prior to the first dose. It is recommended to perform CT or MRI of the chest, abdomen and pelvic cavity at baseline. If there are clinical indications or suspicious lesions in other areas, tumor imaging evaluation must also be performed. Baseline assessment and post-treatment efficacy assessment will be performed using the same method and as much as possible by the same Investigator (RECIST

1.1 criteria, Appendix 1). Tumor imaging assessment (CT or MRI) should be performed every 8 weeks (\pm 7 days) from C1D1 regardless of study treatment status until disease progression, withdrawal of consent, or death, whichever comes first. Subjects who discontinue treatment for reasons other than disease progression or death should continue with imaging assessments per protocol-defined schedule until disease progression, death, or withdrawal of informed consent, whichever occurs first. If the imaging result shows a CR or PR for the first time, it is necessary to repeat the tumor imaging at least 4 weeks later to confirm the response.

Efficacy assessments include ORR (RECIST V1.1 standard) and DCR (RECIST V1.1 standard).

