9.2.1. Analysis Population

Full Analysis Set (FAS)

The FAS will include all subjects who received 3D185 treatment in this study. The FAS will be the primary population for evaluating all efficacy, safety and subject characteristics.

DLT Analysis Set (DLT set)

The DLT set will include all subjects who received at least \geq 75% of the planned doses of treatment and completed the safety assessment during DLT evaluation period. The frequency and severity of DLT will be analyzed.

PK Analysis Set (PKS)

The PK set will include subjects who have received at least one dose and have at least once evaluable PK sample collection after administration.

PD Analysis Set (PD set)

The PD set will include subjects who have received at least one dose and have at least once serum phosphate level measurement (serum biochemistry) after administration.

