9.3. Efficacy Analyses

The Investigator will perform the tumor assessment according to RECIST Version 1.1 at screening and every 8 weeks after the first dose in Cycle 1. The best overall response will be classified into progressive disease, SD, CR and PR. A summary by category and a listing will be provided.

ORR is defined as the proportion of subjects who achieve a BOR of CR or PR in the full analysis set. Estimate of ORR and its 95% exact confidence interval (CI) (Clopper-Pearson) will be provided.

The DCR is defined as the proportion of subjects whose BOR achieve a disease control (CR, PR, or SD) in the full analysis set. Estimate of DCR and its 95% exact CI (Clopper-Pearson) will also be provided.

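### Tumor tissue for FGFR testing is sought only from subjects with CR, PR or SD, so disease control by FGFR status is 100% by construction and response by FGFR status loses its denominator

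*Protocol*

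**What the plan says.** Protocol section 3.3 sets the exploratory objective: "To explore the relationship between the anti-tumor activity of 3D185 monotherapy and the FGFR alterations in subjects with advanced solid tumors". The synopsis lists the matching endpoint: "The relationship between the anti-tumor activity of 3D185 and the tumor FGFR alterations". Neither is limited to subjects who benefit.

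Activity is measured by two rates. Section 7.4.2 states: "Efficacy assessments include ORR (RECIST V1.1 standard) and DCR (RECIST V1.1 standard". Section 9.3 defines both over the full analysis set:

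- ORR: "ORR is defined as the proportion of subjects who achieve a BOR of CR or PR in the full analysis set"
- DCR: "The DCR is defined as the proportion of subjects whose BOR achieve a disease control (CR, PR, or SD) in the full analysis set"

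Section 9.2.1 defines that set: "The FAS will include all subjects who received 3D185 treatment in this study".

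Tissue is handled differently. Section 4.3.2 reads: "For subjects with benefit from receiving 3D185 monotherapy (CR or PR or SD), it is recommended to obtain the disease-related archived tumor tissue". The synopsis (Tumor Tissue Specimen) and note 17 to Table 3 repeat this condition. Sections 7.3.3 and 7.3.4 attach it to the imaging result at C2D28 and at later cycles. Eligibility (section 5.2) requires no FGFR result, and the screening list in section 7.1 contains neither tissue collection nor an FGFR test.

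**The concern.** Tissue collection is triggered by the outcome to which FGFR status is meant to be related. Subjects whose best response is progression, or who have no evaluable scan, are never asked for tissue. They supply the non-events for DCR and part of the denominator for ORR.

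The trial would then be unable to say whether subjects who never achieved disease control had FGFR-altered tumors. The remaining contrast, among benefiting subjects only, could be misread as the overall association. Section 2.3 names selection of subjects by FGFR alteration as a potential advantage of the drug, and this objective is the trial's only planned look at that question. Because the fault lies in data collection, no later analysis plan can correct it.

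**Working it through.** The protocol states no sample size, test or power for this objective, so there is no figure to reproduce. The check is conditional-probability algebra, followed by arithmetic on the protocol's own tables.

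**Step 1. DCR.** Let T be the event that tissue is sought. By section 4.3.2, T = {CR, PR or SD}. By section 9.3, disease control = {CR, PR or SD}. So for any FGFR group g:

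P(disease control | T, g) = 1.

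The difference in DCR between FGFR groups is zero whatever the drug does.

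**Step 2. ORR.** P(CR/PR | T, g) = ORR_g / DCR_g. Each group's ORR is inflated by 1/DCR_g. If DCR differs by FGFR status, the two groups are rescaled by different factors.

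Examples using rates in Tables 1 and 2 (section 2.3):

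| Source | ORR | DCR | ORR/DCR |
|---|---|---|---|
| AZD4547, gastric, n=13 | 7.7% | 7.7 + 30.8 = 38.5% | 20.0% |
| JNJ-42756493, urothelial and other cancers, n=23 | 21.7% | 91.3% | 23.8% |

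The second row is Table 1's "23 evaluable cases, ORR: 21.7%; DCR: 91.3"; its 21.7% includes one unconfirmed PR.

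**Step 3. Subjects without an FGFR result.** Untested = N × (1 − DCR), assuming every benefiting subject supplies usable tissue. The lowest DCR derivable from the tables is 31% (BGJ398 breast cancer: ORR 0, SD 31%). The highest is 91.3%.

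| N | Basis | DCR 31% | DCR 91.3% |
|---|---|---|---|
| 42 | stated maximum | 42 × 0.69 = 28.98 | 42 × 0.087 = 3.65 |
| 32 | i3+3 from 100 mg: 30 + 2 titration | 32 × 0.69 = 22.08 | 32 × 0.087 = 2.78 |
| 48 | 42 + 6 for an added cohort (section 4.1) | 48 × 0.69 = 33.12 | 48 × 0.087 = 4.18 |

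Section 2.3 also gives 22.2% as the lower end of the DCR range. It is not used here. In the tables 22.2% appears only as an SD rate (AZD4547, n=9, PR 33.3%), and 33.3 + 22.2 = 55.5% is the DCR that section 2.1.4 reports for AZD4547 in FGFR2-amplified gastric/esophageal cancer.

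**Step 4. Can the remaining contrast mislead?** Among tested subjects, the odds of response are the CR/PR rate divided by the SD rate. All rates below are assumed.

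| Altered (CR/PR, SD) | Non-altered (CR/PR, SD) | Odds ratio, all treated | Odds ratio, tested only |
|---|---|---|---|
| 20%, 40% | 10%, 20% | (0.20/0.80)/(0.10/0.90) = 2.25 | (0.20/0.40)/(0.10/0.20) = 1.00 |
| 20%, 30% | 10%, 30% | 2.25 | (0.20/0.30)/(0.10/0.30) = 2.00 |
| 15%, 65% | 10%, 20% | (0.15/0.85)/(0.10/0.90) = 1.59 | (0.15/0.65)/(0.10/0.20) = 0.46 |

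The same effect in counts, again assumed: of 42 subjects, 12 are altered (4 responders, 8 with disease control) and 30 are not (3 and 6). Over all treated, ORR is 4/12 = 33.3% versus 3/30 = 10.0%, and DCR is 8/12 = 66.7% versus 6/30 = 20.0%. Under the tissue rule, ORR reads 4/8 = 50% versus 3/6 = 50%, DCR reads 100% versus 100%, and 42 − 14 = 28 subjects are untested.

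**The case against.** The strongest objection is one of weight. The objective is exploratory, and no test, sample size or decision depends on it. MTD rests on DLT and safety data, and the recommended dose on PK, PD and safety. Even with every subject tested, precision would be poor and the comparison confounded by dose and tumor type. All of this stands, and it limits the importance of the point.

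Second, the protocol never announces ORR or DCR by FGFR status; it speaks only of a relationship. That is true, but these are its only two named efficacy rates. What remains possible, such as CR/PR versus SD among benefiting subjects, is neither rate as defined.

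Third, tissue is only recommended, so nothing bars obtaining it from others, and an existing report might sit in a subject's tumor history. No section plans for either, however, and uptake that depends on consent adds further missing results among those who benefit.

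Fourth, 100% is exact only if the rule is followed. An SD call on an early unscheduled scan might fail the RECIST minimum interval (in general 6 weeks). The scheduled scan at 8 weeks ± 7 days falls beyond that interval, so the exception is narrow.

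Finally, the untested range borrows DCRs from other drugs, several in FGFR-altered groups, while this trial is open to any advanced solid tumor. The odds ratios are assumed, and the reversal needs quite different SD rates (65% versus 20%). These figures show what can happen, not what will happen here.

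**Conclusion.** The concern holds. Followed as written, the tissue rule makes DCR uninformative about FGFR status and removes the full-analysis-set denominator from ORR by FGFR status. This follows from the definitions and needs no assumed rates. The subjects lost are those who never reach CR, PR or SD or who have no evaluable scan; subjects who respond or stabilize and progress later remain within the rule.

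The number lost depends on this trial's DCR, which is unknown. Borrowed rates of 31% to 91.3% give roughly 29 down to 4 of 42, and more if consent or tissue fails among benefiting subjects. The direction and size of bias in the remaining within-benefit contrast cannot be predicted; it may be attenuated, null or reversed.

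The damage is confined to one exploratory objective. The change should be made because it is inexpensive and the missing status may be impossible to obtain later.

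**What to change.** Amend the synopsis, section 4.3.2, Table 3 note 17 and sections 7.3.3 and 7.3.4 to request, with consent, archived tissue or an existing FGFR or sequencing report from all dosed subjects regardless of response, ideally at screening. Keep fresh biopsy optional as now. Report best response, ORR and DCR by FGFR status in all subjects with a result, state how many have none, and describe the comparison as exploratory, imprecise and confounded by dose (25 to 300 mg) and tumor type.

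The cost is block retrieval and assay for about 42 subjects, up to 6 more if a cohort is added and any titration replacements, or a CRF field where a report already exists, plus protocol and consent wording. No new biopsy is needed. Some blocks will be missing, and subjects already off study may not be reachable.

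The gain is a valid denominator, not precision. Assume all 42 are tested, 20% are altered (about 8), and DCR is 60% versus 30%. The expected result is then about 5/8 (exact 95% CI 24% to 91%) versus 10/34 (15% to 47%).
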